
2. The central study coordinator will perform off-site eligibility screening of patients across all sites. Responsibilities of the central coordinator may include: 1) Notifying on-site coordinators of upcoming clinic visits of eligible or already enrolled patients 2) Contacting potentially eligible patients to give them information about the study prior to their clinic visit and discussion with an on-site coordinator 3) Contact eligible patients that were missed by on-site coordinators for virtual recruitment and consent 4) Make clinic visits for in -person patient recruitment and consent should onsite coordinators be unable to do so.

When an eligible patient is identified during a clinic visit, they will be approached by a study coordinator who will thoroughly explain the study, provide informational pamphlets, answer any questions, and ensure patient understanding of the study, each device, and their expectations. All study coordinators will have study tablets on which they can access our study website containing an entirely electronic patient enrollment platform, including baseline assessments and consent forms. Interested patients will be given this tablet and asked to review the information and study details and be given ample opportunity to ask any questions they may have. When ready, patients will be asked to read through and sign an e-consent document. Finally, they will be directed to create an account and profilee on our study website.

Eligible patients who have been missed during an in-clinic visit will be contacted by one of the study coordinators by phone. This may be via a phone call or, if unable to reach the patient, via text messaging and/or via e-email through a MyChart message. The following text messaging script will be sent to an eligible patient:

[figure not shown]
You have been selected by your Yale physician to participate in our Yale Heart Failure Digital Health Study. If eligible, you will be:

- compensated for your time
- getting access to new digital tools at no charge to you
- helping us make decisions on what types of tools to offer HF patients

We need your help! Please click on the following link to learn more:

https://yale.digitalhealthstudy.org/about-study

A study team member will be reaching out shortly to provide you with more information. If you have any questions, you can also respond to this text.

The following MyChart message will be sent:

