If you attend one of Yale's Congestive Heart Failure Clinics and are between the ages of 18 and 79, you may be eligible to participate in a free and confidential research study investigating the use of digital health technologies in the care of patients with heart failure. If you enroll, you will potentially receive free access to new digital health tools at no cost to you, and you will be compensated up to \$180 for your time and participation. To learn more or to see if you are eligible to participate, click on "I am interested" or call the Yale Heart Failure Digital Health Study line at [contact]. You can also visit our website at yale.digitalhealthstudy.org for more information.

No action by you is required. You may ignore this message or click "not interested." Thank you very much for considering being a part of research at Yale.

To learn about future research opportunities, you may also create a volunteer profile through the Research Tab in MyChart.

To opt-out of all future research communications, please call the Yale Clinical Trials Office at [name] and select #3.

During an enrollment phone call, the coordinator will discuss the study and instruct the patient through the enrollment process outlined above. The patient will access our study website through a link that will be sent to them via email, text messaging, or other electronic means acceptable to the potential enrollee.

[figure not shown]
Once a patient has electronically consented and created a study profile, an email will be sent with next steps, and will also contain an electronic copy of the signed consent form. They will be directed to complete the KCCQ questionnaire and a medication adherence survey for baseline data collection towards our primary and secondary outcomes, as well as a health literacy assessment and a technology literacy assessment to track any improvements over the course of the study.

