Patients randomized to the control arm of the study will receive usual care only. Patients in the control group will attend their normal clinic visits throughout the first three months of the study as they normally would, however, they will not receive any of the four digital health technologies above and their healthcare team will receive no additional information from any of these products.

Patient Follow-Up and Data Collection

All subjects will be enrolled in the study for a period of 6 months. The first three months will involve active clinic management, and subjects will be seen every 2-3 weeks as clinically indicated for an in-person visit as they normally would outside the research paradigm. Between visits, data regarding device usage, withdrawal rates, and device-generated health data described above will be passively collected from patients in the intervention arms of the trial and stored on a secure HIPAA-compliant database created by Medullan. During clinic visits, patients will also have the opportunity to meet with a study coordinator, who will administer surveys assessing device usability and user satisfaction (for those patients in the intervention groups only), as well as the KCCQ, health literacy and technology questionnaires, and medication adherence surveys (for all patients in the study, regardless of randomization status) to assess changes from baseline.

Once patients have "graduated" from the clinic, they will be followed for the final three months of the study via monthly phone calls from the study team. During this time, passive data collection from devices will continue. At 6 months, subjects will be asked to complete the final surveys appropriate to their randomization group either electronically or via telephone with one of our study coordinators.

Overview and Timeline of the Patient Experience

Day 0

- Patients who have passed initial screening will be approached by site study coordinators at a clinic visit (or via phone call/text messaging) regarding their interest in study participation.
- Study coordinators will describe, in detail, the study protocol with all interested patients, and patients will be asked to provide e-consent via a hippa-compliant, secure website set up for the purpose of the study, after all questions have been adequately answered.
- Consented patients will be asked to fill out a series of surveys and questionnaires used to collect baseline data for the study, including:

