Eligibility will be assessed by on site and central study coordinators who will prospectively review our patient dashboard and further consult the electronic medical record for inclusion and exclusion criteria of patients currently enrolled in the clinics. Criteria will be further confirmed during the patient's in clinic visit or via a telephone call with a study coordinator prior to consent. Digital and technology literacy is not considered an eligibility requirement, as one main goal of the study is to assess whether these digital health products would be efficacious and applicable for this patient demographic. Once a patient has consented to participate in the study and has been enrolled, he/she will be asked to take a digital literacy survey as a means for baseline assessment and to track improvement of this metric over the course of the study.

- 10. **Risks:** Describe the reasonably foreseeable risks, including risks to subject privacy, discomforts, or inconveniences associated with subjects participating in the research. General study risks:
 - Loss of confidentiality: We will be collecting patient information and data, which is subject to loss of confidentiality in any clinical trial.
 - Physician burden: Physicians will be receiving additional information about their patients via the study devices, which may increase workload via additional time spent on patient care, reviewing medical record data, and/or ordering additional tests and reviewing subsequent results.
 - Overtreatment: It is possible that patients in the intervention group may be at risk for more aggressive therapies or treatments and increased medical costs as a consequence of closer monitoring.

Bodyport-specific risks and restrictions:

- The Bodyport scale cannot be exposed to extreme temperatures or submerged in liquid.
- The scale should not be used if the glass surface is cracked or chipped, as this could result in personal injury.
- The scale should not be used of the surface is wet, as this could cause a slippery surface that could result in personal injury.

- 11. Minimizing Risks: Describe the manner in which the above-mentioned risks will be minimized.

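### The recruitment text message promises digital tools to every eligible patient, but one in four randomized patients is assigned to usual care and gets none

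*Combined protocol and SAP*

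**What the plan says.** The text script is in Section I, item 4 (Research Plan), under Subject Eligibility and Recruitment. It opens with "You have been selected by your Yale physician to participate in our Yale Heart Failure Digital Health Study". A list introduced by "If eligible, you will be" follows, and one of its items is "getting access to new digital tools at no charge to you".

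The same subsection says when the script is used. Eligible patients missed in clinic are contacted by phone call or, "if unable to reach the patient, via text messaging and/or via e-email through a MyChart message". Section III, item 3b is looser: it joins phone, text and MyChart with and/or, still for patients whom an on-site coordinator did not see.

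The MyChart message for this group is qualified: "you will potentially receive free access to new digital health tools at no cost to you".

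Under Subject Randomization and Intervention, all consented patients are randomized to one of four arms. "Patients randomized to the control arm of the study will receive usual care only", and "they will not receive any of the four digital health technologies above". (The count of four there does not match the three products being evaluated. That does not affect this point.)

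On who finds the patients, Section I, item 9 states: "Eligibility will be assessed by on site and central study coordinators". They work from the patient dashboard and the medical record. Section I, item 4 and Section III, item 3a describe the same process.

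**The concern.** There are two issues.

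**Accuracy.** The script makes eligibility the only condition for receiving a tool. A patient can be eligible, consent, be randomized and receive none. The protocol sends that statement to patients while holding a more accurate version of it in the MyChart message.

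**Expectation in an open trial.** The study is unblinded, and the primary outcome is the patient-completed KCCQ at day 90. Under Overview and Timeline of the Patient Experience, the Day 0 list puts the baseline KCCQ before randomization. Any reaction to being assigned usual care would therefore act on follow-up scores, not on baseline. It would fall on the one control group that all three device comparisons share. A script that raises the expectation of a tool could add to that reaction.

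The sentence about physician selection is a separate accuracy matter in the same script.

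**Working it through.** **1. Share of patients for whom the promise is untrue.** Inputs from Section I, item 13: target of 200 patients, 50 per arm, four arms.

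- Control share = 50 / 200 = 25%.
- Before the plan's inflation of the sample size: 40 / 160 = 25%.

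So one in four holds either way. No passage offers control patients a tool later. Participation ends at the day 180 close-out.

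**2. The statements side by side.**

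| Place (Section I, item 4) | Condition for getting a tool | Chance assignment or usual care mentioned? |
|---|---|---|
| Text script | Eligibility only | No |
| MyChart message | Enrollment, then *potentially* | Not explicitly, but the qualifier leaves room for it |
| Randomization and control arm | Assignment to one of three device arms | Yes |

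The text script cannot be reconciled with the third row; the MyChart message can. A patient may be sent both messages, because the protocol allows either or both.

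**3. How many trial patients would have seen the text.** Let p be the fraction of randomized patients recruited by text. The share of the whole trial that was promised a tool by text and did not get one is 0.25 × p. The documents do not give p. As assumptions only:

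- p = 10%: 0.25 × 0.10 = 2.5% of patients
- p = 30%: 0.25 × 0.30 = 7.5% of patients
- p = 100%: 25% of patients. This is a ceiling that the described workflow makes implausible, because recruitment starts in clinic and goes next to the phone.

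**4. How an effect would reach the endpoint.** The script comes before randomization, so the expected fraction of controls who saw it is also p. If each such control's day 90 score moved by d points because of the script, the control mean would move by p × d. The documents give neither p nor d, so no size can be computed from them.

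**5. The physician sentence.** The documents have coordinators identify patients from the dashboard and chart review. The treating physician appears in screening once, in the exclusion criteria (item 8), to judge life expectancy. No section describes the physician selecting patients for the study.

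**The case against.** The strongest reply is that the text is a lead-in and not the enrollment step. It gives a link and says that a team member will follow up. Before consent, coordinators explain the study in detail and answer questions. Under Section III, item 7, the coordinator judges whether the patient has understood the study accurately. Randomization comes only after consent, and a patient who wants only a device can decline. The consent form is not among the documents, so one cannot assume that it leaves the impression uncorrected. This stands, and it is the main reason to expect a small effect.

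A second reply also stands. Disappointment at usual care can occur in any unblinded trial, whatever the recruitment route. Only the script's addition to it is relevant here, and nothing in the documents isolates that addition.

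A reader might still infer that the script threatens the primary result, for example by lowering the control mean by 1 to 2 KCCQ points, or 10% to 20% of the 10-point difference the trial targets. The documents do not support this. Such a shift is an assumption, and it is hard to reach through a fallback route. If 10% to 30% of controls had seen the text (again an assumption), a 1-point fall in the mean at p = 30% needs 1 / 0.30 = 3.3 points per texted control, and a 2-point fall at p = 10% needs 2 / 0.10 = 20 points. The upper end is twice the protocol's minimum clinically important difference, and it would have to persist after explanation and consent. The direction is not fixed either: lower self-ratings by controls would inflate device effects, while controls seeking a similar product would dilute them.

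None of this makes the script true or removes its conflict with the MyChart message and the control-arm description.

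**Conclusion.** The point holds as a minor one. The text script states without qualification something that is untrue for one in four randomized patients, and it disagrees with the parallel MyChart message. Its statement about physician selection does not match the screening process described. These conclusions rest on the wording of the documents and on the planned equal arms of 50.

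Any added disappointment among controls is plausible, because the trial is unblinded and the outcome is patient-reported. It is probably small, and the documents do not quantify it. It should not be presented as a bias of known size or direction, nor as reaching every control patient.

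The correction is still worth making. It removes an inaccurate statement to patients and an avoidable source of unequal expectation at very little cost.

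**What to change.** Replace the line about access to tools with a statement of chance assignment, for example: *If you join, you will be assigned by chance to one of three digital tools or to your usual care.* At minimum, carry over the MyChart qualifier *potentially*.

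Replace the physician-selection sentence with one that matches Section I, items 4 and 9, for example: *You may be eligible because you attend a Yale heart failure clinic.*

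Keep the compensation line. Under Section VI, item 2, payment is for completed surveys and does not depend on arm.

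The cost is an amendment to one script and possibly a small fall in response to the text. Sample size, alpha, visits and analysis stay as they are.

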Any clinical data that is collected directly by the device, or any clinical information put into the device directly by the patient (e.g. a daily weight) will be accessible to the patient's physician via device-specific clinician dashboards available to the health care team. Importantly, we do not outline any standardized protocols for physicians to follow regarding use of this data. We will make it clear to all participating physicians that data collected from any device is purely informational and a supplement to regular clinical care. The collected data should not be used on its own to make any clinical decisions. Data must be used by providers in the context of all other clinical information available using their own clinical judgement. Further, the use of these devices should not disrupt usual clinic care in any way. Subjects will continue to see their provider as they would outside of the context of this study and will receive their usual care.

While physicians will have access to all clinical data collected via the devices, we have outlined a limited number of device-specific "triggers", such that when a key datapoint reaches a particular pre-specified threshold, the physician will be notified and asked to follow a standardized protocol in which the healthcare team calls the patient to check in and asks a series of standardized questions to assess the patient's condition and document the responses. We will not provide any pre-specified or standardized protocols beyond these "check-ins" and leave further care decisions up to the discretion and clinical judgement of the patient's

healthcare team. Any decisions made by the provider should be based on all clinical information available in addition to any data provided by a device. These triggers were selected based on the type of information collected by the device and the importance of these data points in the assessment of a CHF patient's status (as determined by our heart failure experts).

The three devices are described below, including the type of data collected and how it is stored, and which clinical data points will be used as triggers to notify the health care team.

Device Based Interventions:

- **BodyPort:** A novel data-driven smart scale that provides advanced cardiac monitoring and risk assessment data that feed directly to an analytics platform visible to providers. The scale also provides limited patient instruction and educational materials.

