The following pre-specified secondary outcomes will be measured to determine the effect of the various technologies on patient outcomes, quality of patient care, clinical efficiency, and both patient and provider satisfaction with the products.

	le l	Patient Outcomes			
	Outcome	Measure	Data Storage		
	Hospital Admissions	Epic, Ping	RedCap (Yale)		
		Rates of prescribing and dosing of beta			
	Guideline directed medical therapy	blockers, ACEi/ARBs, spironolactone (via	RedCap (Yale)		
• • • • • • • •		Surescripts)			
Adverse Events	ED visits	Hospital records	RedCap (Yale)		
	Mortality	Hospital records	RedCap (Yale)		
	Clinic no show rates	Medical records	RedCap (Yale)		
	AKI/AKD Development	Medical records	RedCap (Yale)		
	Satisfaction with device/technology	NPS score via post-study survey	HIPAA-compliant dashboard (Medullan)		
11 h 11	Frequency of use (overall and feature level)	Post-study survey	HIPAA-compliant dashboard (Medullan)		
Usability	Content rating	Post-study survey	HIPAA-compliant dashboard (Medullan)		
	Perceived impact	Post-study survey	HIPAA-compliant dashboard (Medullan)		
	· ·	linician Outcomes			
	Outcome	Measure	Data Storage		
	Amount of intravisit contact	Telephone logs in medical record			
	Number of clinic visits	Medical records			
Clinical Efficiency	Time devoted to patient care	Number of chart openings per patient	RedCap (Yale)		
	Provider assessment of global disease severity	Post-study survey			
Satisfaction	Effect on workload and efficiency	Post-study survey			
		tics of Digital Health Products			
	Outcome	Measure	Data Storage		
Completion of subject enrollment	Number of enrolled patients				
	Number of incomplete enrollments				
Completion rate of baseline assessments	Number of complete and incomplete aseessments				
400000000000000000000000000000000000000	Time to complete initial assessments				
Completion of digital health product set-up	Number of complete and incomplete product set-ups				
product set-up	Number of products that completed initial data sync				
Subject drop-off rates	Percent of patients with last screen assessed in session	Continuous data collection via product	HIDAA compliant dackhoard (Modullan)		
	Number of active (>1 login per week) patients per week	databases	HIPAA-compliant dashboard (Medullan)		
	Average number of logins per week				
	Number of patients without logins per week				
Device usage	Statistic for each session (time of day, day of week,				

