- Risk of overtreatment: The technologies in this study are designed to relay additional information to providers that can be used *in conjunction* with all other medical information available to them to aid in the clinical decision-making process. Any additional tests or treatments should be prescribed using their own clinical judgement based on all available information sources regarding the patient's condition. We will appropriately educate providers about the nature of the study devices and the information that each provides so that physicians can understand how to best incorporate this information into their decision-making.
- Device-specific risks for Bodyport: We will discuss the above risks with the patient before and during the consent process to ensure the patient understand the risks and proper use of the device. The patient will be shown product manuals and informational materials for the scale and will be given the opportunity to answer any questions. Once enrolled into the study and assigned to a treatment group, patients will be given manuals and instructions for the device they receive, and will receive a thorough orientation to the product by a study coordinator who will emphasize any risks involved.
- 12. Data and Safety Monitoring Plan: Include an appropriate Data and Safety Monitoring Plan (DSMP) based on the investigator's risk assessment stated below. (Note: the HIC will make the final determination of the risk to subjects.)

- a. What is the investigator's assessment of the overall risk level for subjects participating in this study? This protocol presents minimal risk to all subjects.
- b. If children are involved, what is the investigator's assessment of the overall risk level for the children participating in this study? N/A
- c. Include an appropriate Data and Safety Monitoring Plan. Examples of DSMPs are available here http://your.yale.edu/policies-procedures/forms/420-fr-01-data-and-safety-monitoring-plans-templates for
 - i. Minimal risk
 - ii. Greater than minimal

Assessing the Efficacy of Digital Health Technology in the Management of Congestive Heart Failure: An Evaluation of Four Novel Digital Health Products

420 FR.1 PI: F. [name] MSCE

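### AKI/AKD is counted from routine records with no scheduled laboratory test, so detection of kidney injury may differ by arm and the plan gives no way to see by how much

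*Combined protocol and SAP*

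**What the plan says.** **Outcome.** The Outcomes table (Section I.4) places "AKI/AKD Development" in the adverse-event group, with medical records as the measure. It gives no threshold, baseline value or time window. The table is introduced with "The following pre-specified secondary outcomes will be measured to determine the effect of the various technologies on patient outcomes", so this is a between-arm effect measure as well as a safety record. The same section repeats the secondary outcomes at day 180.

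**Assessments.** The patient timeline in Section I.4 lists surveys and questionnaires at day 0, day 90 and day 180. No laboratory test is attached to any of these, to the clinic visits every 2-3 weeks in days 1-89, or to the monthly calls in days 90-179. Visits and calls are the same in all arms.

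**Arm-specific information.** The trial is unblinded. Clinicians of device patients see the data and receive trigger alerts; control clinicians receive nothing from the products. On the device data, "we do not outline any standardized protocols for physicians to follow regarding use of this data". A trigger leads to a check-in call, after which the plan is to "leave further care decisions up to the discretion and clinical judgement of the patient's" healthcare team.

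**Foreseen consequences.** Section I.10 says that the extra information may raise physician workload through "additional time spent on patient care, reviewing medical record data, and/or ordering additional tests and reviewing subsequent results", and that intervention patients "may be at risk for more aggressive therapies or treatments and increased medical costs as a consequence of closer monitoring". Section I.11 adds: "Any additional tests or treatments should be prescribed using their own clinical judgement".

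**Analysis.** Section I.13 applies the baseline-comparison tests to outcomes assessed at one time point, which for a yes/no outcome means a chi-square test stratified by clinic. Testing frequency is not considered.

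**The concern.** An outcome that is seen only when someone looks is comparable between arms only if the looking is comparable. Here looking is discretionary, the clinicians know the assignment, and one group of clinicians is given information that the protocol itself says may prompt tests. Recorded AKI/AKD could then differ between arms although kidney function does not.

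AKI/AKD is also the listed outcome that lies closest to the overtreatment risk in Section I.10. More testing and real harm from more aggressive therapy would both raise the recorded count in a device arm. Without a record of how often each arm was tested, a false excess could be taken for harm, and a true excess could be dismissed as detection.

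**Working it through.** The documents give no AKI/AKD rate, test frequency or power for this outcome, so there is no stated figure to reproduce. The check has two parts.

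**1. Can detection differ by arm under the text?**
- Detection needs a test. None is scheduled, so every test is a clinician's decision.
- Inputs to that decision that are equal across arms: visits in days 1-89, monthly calls in days 90-179.
- Inputs that are not equal: device data, trigger alerts and check-in calls (device arms only), and knowledge of assignment.
- In days 90-179 there is no planned visit while device data continue to arrive, so the equalizing effect of visits is weakest there.

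Detection may therefore differ. The text does not say that it will.

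**2. How large could the artefact be with no true difference?**

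Assumed inputs (none from the documents): true risk R = 10%, 20% or 30% in both arms; an episode detectable for D = 14 or 30 days; control patients tested k = 4 or 8 times at random in 180 days; device patients tested m = 1.25, 1.5 or 2 times as often.

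P(recorded) = R × [1 − exp(−kD/180)]

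Spurious risk ratio = [1 − exp(−mkD/180)] / [1 − exp(−kD/180)]; R cancels.

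Worked example with R = 20%, D = 14, k = 4, m = 2:
- Control: kD/180 = 4 × 14/180 = 0.311; 0.20 × (1 − e^−0.311) = 5.3%.
- Device: 8 × 14/180 = 0.622; 0.20 × (1 − e^−0.622) = 9.3%.
- Risk ratio 1.73, difference 3.9 points, with identical kidney function.

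| Extra tests in device arm | Spurious risk ratio |
|---|---|
| none | 1.00 |
| 25% | 1.10-1.21 |
| 50% | 1.17-1.39 |
| 100% | 1.26-1.73 |

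Over the whole grid the spurious difference is 0.5 to 7.5 percentage points.

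For days 90-180 alone, with 1 or 2 control tests and 50% to 100% more in the device arm, the same formula with 90 in place of 180 gives ratios of 1.30 to 1.86. Sparse testing makes the relative gap larger, which is a reason to report test counts by period.

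**Chance of a false significant excess.** For one device arm against control (50 vs 50), with a normal approximation, no clinic strata and an assumed two-sided 0.05, the chance of declaring more AKI in the device arm is about 3% to 16% over the grid, and about 11% in the worked example. With equal testing the nominal rate in that direction is 0.05/2 = 2.5%. Expected counts are small (5.3% of 50 is about 2.7 control patients in the example), so these rates are approximate.

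**The case against.** The strongest reply is that the protocol promises little of what the concern needs.

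- **Wording.** Extra testing appears in a disclosure of possible physician burden. It says may, and names neither creatinine nor any blood test. A reader might infer that the protocol expects more creatinine tests in the device arms; it does not say so. The protocol also says that the devices should not disrupt usual care, and the only standardized response to a trigger is a call. This stands: the claim has to be that detection may depend on arm.
- **Equal contact.** Visits and calls do not depend on assignment, and the plan already records clinic visits, telephone contact and chart openings. This stands in part. Equal contact narrows the gap, and those measures hint at intensity of care, but none of them counts kidney tests.
- **Three different products.** BodyPort supplies new physiological measures, including fluid-related ones that may serve as triggers. Noom relies on entered or synced data. Conversa measures nothing new and may trigger on symptoms. A single testing increase for all device patients is unsupported. This stands.
- **Size.** If every test is treated as an independent 2% chance of a qualifying rise, then 4, 6 and 8 tests give 1 − 0.98^4 = 7.8%, 1 − 0.98^6 = 11.4% and 1 − 0.98^8 = 14.9%, or ratios of 1.47 and 1.92. That model lets recorded AKI grow almost in proportion to tests. With a finite episode and a fixed true risk, the ratios for the same increases are 1.17-1.39 and 1.26-1.73. The larger figures should not be relied on.
- **Hospital-only comparison.** A reader might conclude that the between-arm comparison should move to AKI found at ED visits or admissions. Those visits are themselves outcomes that the products may change, and outpatient injury, where overtreatment could show, would be lost. Such an analysis is useful as a sensitivity analysis only.

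**Conclusion.** The concern holds in a limited form. AKI/AKD is a prespecified between-arm outcome with discretionary, unblinded ascertainment, and the protocol itself names a route by which testing could increase in the device arms. The plan neither measures nor allows for this.

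The size is unknown. The range of about 1.1 to 1.7 for the spurious risk ratio rests wholly on the assumed risks, episode durations and test counts, and on tests falling at random times. It shows what unequal testing could do, not what will happen. At 50 per arm the main effect is a distorted estimate; a false significant excess is possible but unlikely.

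The documents do not support the stronger reading that any AKI excess in a device arm would be an artefact. Section I.10 names more aggressive therapy as a risk, so an excess could be real, and the design as written cannot tell the two apart. The KCCQ primary outcome, its sample size and the stopping rule are not affected. This is a cheap improvement, not a flaw that threatens the trial.

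**What to change.** 1. Keep all-records AKI/AKD as the outcome. Define it by one prespecified creatinine rule against the last pre-randomization value, applied to laboratory values in the same way in all four arms.
2. Beside the AKI comparison, report creatinine tests per patient and the proportion of patients tested, by arm, for days 0-90 and days 90-180. Show the three products separately.
3. Add a prespecified sensitivity analysis limited to AKI identified at an ED visit or hospital admission, noting that such visits may themselves differ by arm.
4. State in Section I.13 that an AKI difference accompanied by unequal testing will not, on its own, be interpreted as a product effect.

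**Cost.** One more count to abstract; Section IV already lists laboratory values and hospital records among the data collected. The sensitivity analysis will have few events, and the AKI conclusion will be more cautious. No blood draws are added. Creatinine at the same fixed times in all arms would address the bias more directly, but would add sampling to a study that has none; the steps above do not require it.
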